This protocol reflects similar procedures to previously approved protocol #53545; however, instead of being conducted in the PI's lab space, this study will take place at in UK Psychiatry's Adult Outpatient clinic. The primary purpose of this study is to explore whether the efficiency of treatment for anxiety and depressive disorders can be increased using two discrete strategies: personalized skill ordering and 2) treatment discontinuation based on proximal indicators of improvements. The present study will specifically use treatment components drawn from an evidence-based psychological intervention, the Unified Protocol for the Transdiagnostic Treatment of Emotional Disorders (UP; Barlow et al 2011; 2018). This intervention has strong empirical support for patients presenting with anxiety, depressive, and related disorders (see: Barlow et al., 2017) and contains therapeutic skills that are common in psychological interventions (e.g., psychoeducation, mindfulness training, cognitive restructuring, counteracting emotional avoidance, increasing interoceptive tolerance). Skill modules in the UP are typically delivered in a standard order. Recent research conducted by the PI has shown that each UP module, when presented in isolation, leads to change in its associated skill (e.g., the mindfulness module leads to increased mindfulness), as well as improved symptoms ([name] et al., 2017). Given this evidence that each skill is self-contained, the PI recently conducted a pilot study personalizing the sequencing of UP modules ([name] et al., 2019). Specifically, a small sample (n=12) was randomly assigned to receive UP skills in an order that prioritized relative strengths vs. relative weaknesses. Results suggest that it is feasible to order modules in this manner, that patients were satisfied with their personalized order, and that, by the final session, patients in both conditions demonstrated similar levels of symptom improvement (comparable to effects for the standard presentation of the UP). There was also preliminary evidence to suggest that capitalizing on patient strengths is associated with steeper trajectories of change (i.e., faster symptom improvement) compared to compensating for deficits.

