In this 3 x 2 design, patient participants (N = 150) will be randomly assigned to receive treatment modules sequenced according to the following three module-ordering conditions: 1) Standard: In accordance with the standard, published UP manual; 2) Capitalization: organized to prioritize skills that capitalize on patient strengths; 3) Compensation: organized to prioritize skills that compensate for patient weakness. All participants will also be randomized to two treatment-duration conditions: 1) Brief: 7 sessions; or 2) Full: 13 sessions. Deception will not be used – patients will be fully informed about the possibility of being assigned to the Brief or Full treatment length condition. However, during the consent process, we have elected to limit the information provided about each ordering scheme. Instead, participants will be told that we may use their self-report questionnaire data to determine the order of their skills. This omission of information is justified for the following reasons: 1) knowing their condition may bias results and, given that the conditions are face valid, patients may be able to guess their assignment if they are provided detailed information about the possibilities, and; 2) although research provision of manualized interventions (like the UP) are typically delivered in a standard order, it is common in routine practice for therapists to make decisions about how to order treatment skills without providing patients with reasoning. Following the final assessment, patients will be provided with information about the three module-ordering conditions and the condition to which they had been assigned will be revealed.

Clinician participants will not be randomized - all clinicians will be asked to attend a training workshop in the Unified Protocol and participate in weekly consultation calls with [name] or [name]. They will provide care in each patient condition (standard, capitalization, compensation; brief, full). Clinicians will be asked to complete surveys and interviews about their impressions participating in this study/providing care based patient strengths/weaknesses.

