Likely eligible participants, determined by the phone screen, will be invited to attend an in-person session at UK Psychiatry or a virtual session using either UKHealthCare HIPAA-compliant Zoom or phone (Assessment Visit 1). As described above (see "Informed Consent" section), a study assessor (i.e., doctoral students in clinical psychology/post-doctoral scholar) will review study procedures with potential participants and ask them to provide their informed consent. After informed consent is provided, an interview-based diagnostic assessment will be administered in order to confirm clinical inclusion/exclusion criteria, as well as to provide a baseline level of clinical severity. This assessment visit will be audio-recorded provided participants give their consent for this. Next, patients will be asked to complete a battery of self-report questionnaires, which will assess symptoms of anxiety/depression, level of functioning (i.e., clinical interference, quality of life), and proficiency in the skills taught during treatment with the UP. Those that are deemed ineligible after this assessment will be withdrawn, whereas we will work with eligible participants to schedule their next study session (Treatment Session 1). After Assessment Visit 1, study staff (i.e., research assistant) will randomly assign them to one of three module-ordering conditions: Standard (modules order according to the published manual), Capitalization (modules ordered to prioritize patient strengths) and Compensation (modules ordered to prioritize patient weaknesses). The completed self-report battery from Assessment Visit 1 will be used to order modules for those assigned to the Capitalization and Compensation conditions. Study therapists (i.e., clinicians at UK psychiatry), study assessors (i.e., doctoral students in clinical psychology/post-doctoral scholar), and participants will be blind to module-ordering condition.

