We will use a treatment window during which the assigned number of sessions will be completed; specifically, patients randomized to the Brief condition will complete 7 sessions during an 10-week window and patients randomized to the Full condition will complete 13 sessions during a 20-week window. This will allow us to account for scheduling challenges (e.g., patient/therapist illness, vacation). The first session for all participants will be an "orientation to treatment" session in which presenting concerns will be reviewed and an overview of the treatment model will be provided. As noted previously, the skills delivered during the remaining sessions in this study will be drawn from the UP. Four of the five UP modules will be implemented 2 sessions: Understanding Emotions, Mindful Emotion Awareness, Cognitive Flexibility, and Increasing Interoceptive Tolerance. The 5th UP module, Countering Emotional Behaviors, is designed to be implemented in 4 sessions. All sessions will last for 60 minutes in duration. Thus, depending on treatment length and module order, each participant will receive 2 to 5 UP modules during this study. It is important to note that the therapeutic strategies involved in all modules are all common, evidence-based cognitive-behavioral strategies and are not, themselves, under study; instead, we are interested in whether personalized sequencing leads to faster improvements (not whether patients improve at all - we expect that most will improve). Every module involves reading from a published manual (the Unified Protocol for the Transdiagnostic Treatment of Emotional Disorders; Barlow et al., 2018) and completing homework assignments outside of the treatment session (this intervention has previously been reviewed by UK's non-medical IRB). These treatment sessions will be audio-recorded provided participants give their consent for this; this will allow study staff to rate sessions for fidelity to the protocol.

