Clinician Participants will be asked to attend a one-day training workshop on the Unified Protocol. The PI, [name], was the founding director of the Unified Protocol Institute in her previous academic position at Boston University; in this role, she routinely provided this training, which will consist of didactic lecture and role plays. After the workshop, clinicians will be asked to begin implementing the UP with patients on their caseload that have consented to participate in this study. Clinicians will also attend weekly consultation calls with the PI who will provide additional guidance on the delivery of the study intervention; clinicians will be asked to participate in these calls for the duration of time they have study patients on their caseload. Clinicians will be asked to audio-record their work delivering the UP with their study patients; these tapes will be rated for adherence and competence with the protocol (see attached adherence checklists that study staff will use to rate tapes). Study staff will provide clinicians these audio-recorders for the duration of the study; study staff will stop by clinicians' offices to pull recordings off the audio recorder and upload them directly to the UK provided, password-protected TIPS lab server space. Finally, clinicians will be asked to fill out questionnaires at several time points during the study: 1) directly following provision of their informed consent, 2) following completion of the didactic workshop, and 3) after all patient treatment has been completed. Following their provision of informed consent, all questionnaires will be collected via an email with a link to an online REDCap survey.

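### Therapists are declared blind to module order, but they deliver the sequence themselves and the published manual's order defines Standard, so they cannot be reliably blind to Standard versus personalized order

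*Combined protocol and SAP*

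**What the plan says.** The blinding statement in Research Procedures covers three groups: "Study therapists (i.e., clinicians at UK psychiatry), study assessors" and, at the end of the sentence, "and participants will be blind to module-ordering condition". It appears just after the arms are defined, including "Standard (modules order according to the published manual". Study Design defines that arm the same way: "In accordance with the standard, published UP manual".

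Other parts of the Research Description bear on what a therapist can see:

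- Background: "Skill modules in the UP are typically delivered in a standard order".
- Study Design, on clinicians: "They will provide care in each patient condition (standard, capitalization, compensation; brief, full".
- Research Procedures, on training: "Clinician Participants will be asked to attend a one-day training workshop on the Unified Protocol". Weekly consultation calls follow for as long as the clinician has study patients.
- Research Procedures, on content: "Every module involves reading from a published manual". The order of skills in the weekly sessions is set by the ordering arm, and each patient receives two to five of the five modules.

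Patients are told that one of three ordering methods will be assigned by chance and that their questionnaire answers may be used to set the order. The schemes themselves are withheld until after the final assessment, because the plan considers them face valid and open to guessing.

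In the Statistical Design section, the primary outcome for the sequencing question is the MEAQ distress aversion subscale (MEAQ-DA). Data Collection lists the MEAQ in the patients' weekly pre-session battery. The statistical text does not mention masking.

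**The concern.** Blinding a person to a condition requires that the condition not be visible in what that person does. Here the condition is the order of the modules, the therapist carries out that order, and the reference arm is the order of the manual used in treatment. The documents describe no way of hiding the manual's order from therapists, and no check of what they believe the assignment to be.

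What is at stake is how a difference between Standard and the personalized arms may be read. MEAQ-DA is a patient self-report collected during treatment, and a therapist who knows that an order was tailored may convey more confidence or deliver the modules differently. The plan takes this kind of threat seriously elsewhere: it delays the treatment-length randomization to limit expectancy effects in therapists and participants. For module order, the therapist-side safeguard described is the blinding statement. If that statement is carried into a report or into the design of the larger trial, a contrast open to therapist expectancy will be described as masked.

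**Working it through.** The documents give no figure for blinding, so there is none to reproduce. The check has a logical part and an illustrative part.

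**Logic.** (a) Standard is the manual's order. (b) The therapist knows the delivered order, having delivered it. (c) The manual is part of every module. From these, an order that differs from the manual's cannot be Standard. This step needs no assumption about how personalized orders are distributed. Only a delivered order that coincides with the manual's so far is ambiguous.

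**Illustration.** Inputs:

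- Five modules (Research Procedures).
- Three ordering arms. The allocation ratio is not stated; 1:1:1 is assumed.
- Personalized orders: the distribution is not stated. All 5! = 120 orders are first taken as equally likely, and that assumption is then varied.

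Let m be the chance that a personalized order agrees with the manual through the first k modules. Under uniform orders m = 1/5, 1/20, 1/60 and 1/120 for k = 1, 2, 3 and 4 or more. By Bayes' rule,

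P(Standard | match) = (1/3) / [(1/3) + (2/3)m] = 1 / (1 + 2m).

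If every match is called Standard and every departure personalized, the proportion classified correctly is 1/3 + (2/3)(1 − m).

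| Modules seen | m | P(Standard given match) | Correct overall |
|---|---|---|---|
| 1 | 0.200 | 71% | 87% |
| 2 | 0.050 | 91% | 97% |
| 3 | 0.017 | 97% | 99% |
| 4 or 5 | 0.008 | 98% | 99% |

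**Sensitivity at two modules.** Personalized orders come from baseline questionnaires and need not be uniform. If 20% of them shared the manual's first two modules, P(Standard | match) = 1/(1 + 0.40) = 71%. At 30% it is 1/(1 + 0.60) = 63%. The converse inference does not change: a departure still means personalized.

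**Which rows apply.** After orientation, a 7-session course leaves six skill sessions. With four modules of two sessions and one of four, that reaches two or three modules. A 13-session course leaves twelve, which covers all five. Brief patients therefore never reach the last row, but every patient reaches the second.

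**The case against.** The strongest reply is that the blinding that matters most for a self-reported outcome is the patient's, and the documents do not show that it fails. Patients are not told during treatment that one of the three methods is the manual's own order. The text does not say in what form they receive the manual. This stands. A reader might infer that anyone who sees the sequence can name the arm, or that these contrasts are open-label; the documents support neither. For patients, the most that can be said is that masking is partial and untested.

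Second, the text says only that the workshop is on the Unified Protocol, so training in the published order is an inference. The survey of clinicians about strengths- and weaknesses-based care is weak evidence of what they know during treatment, because the provider feedback form comes after their last study patient. Both points are fair. The argument needs neither, since delivering the sequence alongside the manual is enough.

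Third, it is tempting to conclude that Capitalization versus Compensation is a properly masked contrast. Order alone does not separate those two arms, but the plan itself calls the conditions face valid, and a therapist may see whether strengths or weaknesses are being addressed first. Nor is assessor masking verified: under Resources, the people who conduct assessments also support the clinicians. That does not show that assessor masking fails.

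Fourth, this is a pilot whose primary aim is feasibility and acceptability, and the sequencing comparison seeks only a preliminary signal. That limits the consequence but does not remove it, because the signal is meant to inform whether further testing is warranted.

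**Conclusion.** The statement that therapists are blind to module-ordering condition is wrong as written for Standard versus personalized order. That a departure from manual order reveals a personalized arm follows directly from the plan's own definitions. How strongly a match points to Standard depends on assumptions that the documents do not supply: at two modules it is 91% with uniform orders and 1:1:1 allocation, and 71% if a fifth of personalized orders begin as the manual does. Recognition is probable rather than certain.

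The finding extends no further. Patient unblinding is plausible but not demonstrated, failure of assessor blinding is not shown, and masking of Capitalization versus Compensation is neither established nor refuted. The practical consequence is a limit on interpretation: therapist or patient expectancy remains a possible explanation for any Standard-versus-personalized difference on MEAQ-DA.

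**What to change.** 1. In Research Procedures, replace the blinding sentence. State that therapists and patients are not told the ordering condition, that therapists can probably recognise whether an order is Standard or personalized, and that assessors are intended to be masked.
2. In the Statistical Design section, where MEAQ-DA is named, add that Standard-versus-personalized contrasts are not reliably therapist-masked and that therapist or patient expectancy is a possible explanation for a difference. Do not describe Capitalization versus Compensation as a verified masked contrast.
3. Where patients or clinicians are still reachable, add one condition-guess item to the existing feedback forms. The forms are attachments not shown here, so check first whether perceived condition is already asked. The clinician feedback form is completed once per caseload, so the guess would have to be recorded for each patient.

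The first two changes cost only wording and a less favourable description of blinding. The third may yield little: the continuation review reports 50 patients enrolled and none newly reported, and enrollment was planned to end by January 2023. The first two are worth making even if no guesses can be collected. No treatment procedure changes.

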#### Attachments

Attach Type	File Name
ResearchProcedures	Clinician Participant Recruitment Email Template.docx

ResearchProcedures	[name] LOS.pdf
ResearchProcedures	UP Adherence Rating Forms (1).doc
ResearchProcedures	Phone Screen Script.docx
ResearchProcedures	Phone Screen_4_30_20.docx

### Data Collection & Research Materials

In this section, please provide the following:

- Describe all sources or methods for obtaining research materials about or from living individuals (such as specimens, records, surveys, interviews, participant observation, etc.), and explain why this information is needed to conduct the study.
- For each source or method described, please list or attach all data to be collected (such as genetic information, interview scripts, survey tools, data collection forms for existing data, etc.).
- If you will conduct a record or chart review, list the beginning and end dates of the records you will view.

Data collection will be accomplished via phone screening questions, diagnostic interview, and self-report questionnaires attached below. Through these measures we will collect data regarding participants' experiences with psychological symptoms, life functioning, and interpersonal interactions throughout the study.

The measures will be administered to patients according to the following schedule:

Assessment Visits:

DIAMOND

Demographic form (A1 only)

OASIS

ODSIS

UCLA Loneliness-3

DASS

WSAS-CR

Q-LES-Q

MEAQ

PANAS

BES

SMQ

ASI

PAI-BOR

NEO-FFI

EPQR-S

IIP-BPD

NEO-PI-R-N

CBTSQ-BA

Hope Scale

Medication list (Assessment Visit 1 only)

Concurrent Treatment Form (Assessment Visits 2, 3, and 4 only)

Feedback Form (post-Assessment Visit 3 only)

URICA (Assessment Visit 1 only)

Decision-making self-efficacy scale (Assessment Visit 1 only)

Initial Treatment Preferences Questionnaire (Assessment Visit 1 only)

C-SSRS - Full measure

HAM-A

HAM-D

CSQ-8 (Assessment Visit 3 only)

Patient Post-Treatment Feedback Form (Assessment Visit 3 only)

Pre-Session (Weekly):

OASIS

ODSIS

UCLA Loneliness-3

MEAQ

PANAS

BES

SMQ

CBTSQ-BA

MEAQ-BA

ASI

Self-perception of Skill Use

C-SSRS items 1-6

UP-CSQ

Post-Session (Weekly):

WAI-SR  
CEQ (post-1st session only)

The following measures will be administered to clinicians according to the following schedule:

During initial visit (after informed consent):

EBPAS  
Motivation to Learn Scale  
Therapist Demographics

After the didactic workshop:

Post workshop provider feedback  
Therapist Knowledge Acquisition quiz

After each patient has completed treatment:

CGI

After all study patients on the clinician's caseload completes their last session:

Provider feedback form

Qualitative Interviews for:

Patient Participants  
Clinician Participants

Because focus groups for Patient Participants and Clinician Participants will occur 9-12 months after the conclusion of treatment, and because the questions involved in these focus groups will be based, in part, on the information gleaned from the post-study qualitative interviews, focus group questions are not available at this time. This is standard practice in qualitative research, and before beginning any focus group activities, we will submit the proposed questions to the IRB for approval via a Modification Request to ensure these questions respect participant safety and privacy. Given that these focus groups will include multiple Clinician Participants, we will include language clearly specifying that participants should not discuss information about patients that would constitute PHI.

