Regardless of randomization, all participants will be scheduled for Assessment Visit 2 to occur between treatment sessions 5 and 6. Participants will complete an interview-based diagnostic assessment with a study assessor that will focus on the diagnoses assigned at Assessment Visit 1. This assessment may take place in person at UK psychiatry, over the phone, or via HIPAA-compliant Zoom. This assessment visit will be audio-recorded. Participants will also complete the same battery of self-report questionnaires at this visit as at Assessment Visit 1. All participants will also complete Assessment Visit 3, which will take place between weeks 13-16 (corresponding to the end of the treatment window for the Full length condition). This assessment visit will also be audio-recorded and may take place in person at UK Psychiatry, over the phone, or via HIPAA-compliant Zoom. Finally, Assessment Visit 4 will take place (in person at UK Psychiatry, over the phone, or via HIPAA-compliant Zoom) between 46 and 50 weeks after Assessment 1 and will include the same questionnaires.

Following the last treatment session (Treatment Session 13 for participants in the Full treatment condition; Treatment Session 7 for participants in the Brief treatment condition), participants will be asked to provide satisfaction ratings and written qualitative feedback on their experience with the treatment they received. Additionally, all participants will be asked to complete a weekly self-report battery assessing symptoms, skill proficiency, and skill knowledge for 20 weeks (again corresponding to the treatment window for the Full length condition); patients in the Brief condition will continue to complete these questionnaires after discontinuing treatment. These questionnaires will be emailed to participants and we will ask that they are completed within two days of receipt.

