## Statistical Design and Power

### Statistical Design

**Study Feasibility.** Clinician and patient enrollment, a measure of feasibility of a large RCT, will be assessed by reporting percentages for the 6 clinician and 5 patient enrollment variables. Rates of treatment and assessment completion will also be reported. Clinician adherence will be evaluated by coding 20% of treatment sessions according to a UP adherence checklist and reporting adherence rates within each condition.

**Study and Treatment Acceptability.** Quantitative measures of study and treatment acceptability (e.g., the AFQ, Clinician and Patient Versions) will be assessed through the use of descriptive statistics. Qualitative analyses of clinician and patient perceptions of study and treatment protocols will be analyzed in conjunction with quantitative results (e.g., QUAL + QUAN). Qualitative analysts will review interview recordings and transcriptions, identifying and coding the primary issues raised by respondents using a grounded theory, embedded in Willms, et al.'s guidelines for coding: reaching consensus on coding assignment, identifying concordance among codes, and using the process of constant comparisons to generate a taxonomy of themes and identify their relationships to one another. This will have analysts: 1) review all transcripts to develop a broad understanding of the content and document initial impressions of topics and themes, defining the boundaries of specific codes, 2) independently code empirical material to condense data into analyzable units and form a codebook, 3) discuss disagreements in code assignment/description (each test will be reviewed by at least two analysts), 4) compare reliability of assigning the same codes to identical text segments, and 5) use the computer program *NVivo* to examine the association between different a priori and emergent categories.

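### Patient satisfaction is due after each patient's own last session in one section and at Visit 3 only in another; if the visit schedule is followed, the timing of the rating depends on treatment length

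*Combined protocol and SAP*

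**What the plan says.** Research Procedures sets the first timing. Once a patient's final session is over, which is session 7 in the Brief arm and session 13 in the Full arm, the section states: "participants will be asked to provide satisfaction ratings and written qualitative feedback on their experience with the treatment they received". The anchor is the patient's own final session, so it falls at a different calendar point in each treatment-length arm.

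The measure schedule in Data Collection & Research Materials sets the second. Under Assessment Visits it lists "CSQ-8 (Assessment Visit 3 only") and "Patient Post-Treatment Feedback Form (Assessment Visit 3 only"). It also has a further entry, "Feedback Form (post-Assessment Visit 3 only"), and does not say whether this is the same form or another one.

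Research Procedures gives everyone the same window for that visit: "Assessment Visit 3, which will take place between weeks 13-16 (corresponding to the end of the treatment window for the Full length condition"). The same section says that "patients randomized to the Brief condition will complete 7 sessions during an 10-week window" and that Full patients have 13 sessions in a 20-week window.

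On analysis, Statistical Design says "Quantitative measures of study and treatment acceptability (e.g., the AFQ, Clinician and Patient Versions") will be summarised with descriptive statistics. The SAP's paragraph on the pilot test of personalization names feasibility and acceptability jointly as the primary aim.

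**The concern.** The two timings are different measurements. One asks for a judgement when treatment ends. The other asks at a common calendar point, when a Brief patient has already stopped and a Full patient may not have finished.

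Under the second timing, treatment length determines how long ago treatment ended. A Brief patient's rating then reflects the treatment, the fading of recall, and whatever happened to symptoms after stopping. The SAP itself expects that some discontinued patients may go on improving without treatment. Some Full patients would complete a form with post-treatment in its title while still in treatment. Anyone who lays the Brief and Full summaries side by side to judge whether shorter treatment is acceptable would be comparing ratings made at different stages.

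**Working it through.** The documents give no figure for this delay, so there is nothing to reproduce. The check is interval arithmetic.

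**Inputs (Research Procedures)**
- Visit 3: weeks 13 to 16, all patients.
- Brief: 7 sessions within 10 weeks. Full: 13 sessions within 20 weeks.

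**Assumptions**
- Weeks are counted from the start of treatment. The documents give no origin for weeks 13-16.
- There is at most one session a week, so the last session falls in weeks 7-10 (Brief) or 13-20 (Full).

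**Formula**
- Delay = week of rating minus week of last session.
- Smallest delay = earliest rating minus latest last session. Largest delay = latest rating minus earliest last session.

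**If the forms are given at Visit 3 only**
- Brief: 13 − 10 = 3 to 16 − 7 = 9 weeks after the last session.
- Full: 13 − 20 = −7 to 16 − 13 = +3, that is, from 7 weeks before to 3 weeks after the last session.
- The two ranges meet only at 3 weeks.
- Strict weekly pace: Brief 13 − 7 = 6 to 16 − 7 = 9 weeks; Full 13 − 13 = 0 to 16 − 13 = 3 weeks. The gap between arms is 13 − 7 = 6 weeks.

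**If the forms follow each patient's own last session**
- The delay is about 0 in both arms. What differs is time since the start of treatment: weeks 7-10 for Brief, weeks 13-20 for Full.

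**Sensitivity**

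| Rating time | Sessions (Brief/Full) | Brief delay | Full delay |
|---|---|---|---|
| Weeks 13-16 | 7/13 | +3 to +9 | −7 to +3 |
| Weeks 13-16 | 6/12 | +3 to +10 | −7 to +4 |
| Week 20 | 7/13 | +10 to +13 | 0 to +7 |
| Week 20 | 6/12 | +10 to +14 | 0 to +8 |

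The 6/12 rows are included because Research Procedures also states those session counts when it describes the second randomization. The week-20 rows are included because the SAP refers to a W20 assessment and the Full window ends at week 20. At a strict weekly pace the gap between arms is 6 weeks in every row.

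**Can the two passages be read as one?** For Brief patients, loosely, yes: Visit 3 does come after session 7. For Full patients, no: anyone whose session 13 falls in weeks 17-20 reaches Visit 3 before treatment ends, so a rating at that visit cannot follow the last session.

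**The case against.** Several points on the other side stand.

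- **The unequal delay is conditional.** A reader might infer that acceptability is measured at different delays by arm. That follows only if the visit schedule governs. Under the last-session rule the delays are about equal, and the documents do not say which applies.
- **No planned test is affected.** The SAP specifies descriptive statistics combined with qualitative findings, and no Brief-Full contrast of acceptability. Treatment length is itself randomized, so any length-related delay should balance on average across the three ordering conditions.
- **It is not the whole primary aim.** That aim is joint. It also rests on enrolment, treatment and assessment completion, adherence, interviews, and clinician data, whose timing does not depend on Visit 3. The third objective under Objectives concerns acceptability to clinicians.
- **The early Full ratings come partly from another conflict.** Weeks 13-16 are described as the end of the Full window, which is elsewhere 20 weeks. At week 20 no Full patient rates early, although the gap between arms remains. The values −7 and +9 are extremes.
- **A common calendar visit has merit.** It equalises time since the start of treatment, which the last-session rule does not. The plan gives no such rationale, however, and its procedures text says otherwise.

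A reader might also infer from the SAP's AFQ that the acceptability measure is never collected. No form of that name is in the schedule or the list of attached data-collection files. But it is introduced only as an example, and the patient and clinician feedback forms that are listed could be the same instrument under another name. It has no bearing on the delay. Nor do the documents rank the acceptability measures, so they do not support making the CSQ-8 the headline score.

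**Conclusion.** The contradiction is real and should be resolved, because it leaves open when a patient-rated outcome is collected. If the visit schedule is followed, Brief patients rate 3 to 9 weeks after treatment and Full patients from 7 weeks before to 3 weeks after it. If the visit is at week 20, the delays are 10 to 13 weeks against 0 to 7. These figures rest on counting weeks from the start of treatment with at most one session a week. The 6-week gap further assumes that no week is missed.

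The consequence is limited to interpretation: patient satisfaction could not be read cleanly by treatment length. The documents do not support the stronger conclusions that the delay difference is certain, that a planned comparison is biased, or that the primary aim as a whole fails.

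**What to change.** 1. Align the measure schedule with Research Procedures: send the CSQ-8 and the Patient Post-Treatment Feedback Form by REDCap email after each patient's own last session. REDCap emails already go to patients weekly for 20 weeks, so this needs one more trigger and a wording change.
2. State what the separate feedback-form entry after Visit 3 is, and whether it duplicates the patient form.
3. For patients already rated at Visit 3, report satisfaction by treatment length together with the time since last session, and flag ratings made before treatment ended. The continuation review records 50 enrolled and none newly reported, so this may be the part that matters most. It requires only the session and rating dates.
4. As a minor traceability point, say in Statistical Design which scheduled forms are the clinician and patient versions of the AFQ.

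The passages on session counts (7/13 and 6/12), and those on the end of the Full window against the timing of Visit 3, also need to be reconciled. This review takes no view on which is right.

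Costs: under the last-session rule, time since baseline differs by arm, and if some patients have already been rated at Visit 3 the data will hold two timings. Both are manageable if each rating's delay is reported.
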